**11.4.5.4 12-lead ECG**

ECG interpretation (normal vs. abnormal) will be summarized using frequency and percentage at each visit by treatment group. ECG intervals (PR, QT, HR, and QTcF) will be summarized descriptively at each visit. The number and percentage of patients with exceeding pre-defined absolute and relative threshold values will be summarized (Table 7).

When calculating the percentages for the criterion related to a threshold, the numerator will be the number of subjects with normal baseline with respect to the specific criterion and at least 1 post-baseline outlier value within the analysis period; and the denominator will be the number of subjects with a baseline and at least 1 post-baseline assessment within the analysis period.

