### **Medical Conditions or Diseases**

8. Expected to require blood transfusion within 12-weeks post-randomization.
9. Thromboembolic event within 12-weeks prior to randomization.
10. Clinical evidence or suspicion of active infection.
11. History of peptic ulcer disease or gastrointestinal ulceration in the 12-months prior to randomization.
12. History of active diverticulitis in the 12-months prior to randomization.
13. History of inflammatory bowel disease that has been clinically active during the 12-months prior to randomization.
14. Uncontrolled hypertension (defined as an average SBP  $>160 \text{ mmHg}$  or an average diastolic blood pressure (DBP)  $>100 \text{ mmHg}$  during screening. Patients may be re-evaluated within 2 weeks, at the discretion of the investigator for this criterion if anti-hypertensive therapy has been started or increased as a result of initial screening blood pressure being above these limits.
15. Planned coronary revascularization (PCI or CABG) or any other major surgical procedure.

16. Major cardiac surgical, non-cardiac surgical or major endoscopic procedure within the past 6 months prior to Randomization.
17. History of New York Heart Association Class IV congestive heart failure within 12-weeks prior to randomization.
18. Actively treated or active malignancy during the 1-year prior to randomization with the exception of successfully treated nonmetastatic basal cell or squamous cell carcinomas of the skin and/or local carcinoma in situ of the cervix.
19. History of bone marrow or solid organ transplant or anticipated to receive an organ transplant during the time frame of the study.
20. Known allergy to the study drug or any of its ingredients.

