### 11.1 Sample Size

The primary efficacy endpoint is percent change from baseline in hs-CRP (average of the hs-CRP value prior to randomization and Day 1) to Week 13 between each active group and placebo. Based on the observed treatment difference in percent change from baseline in hs-CRP of -60.74% between combined COR-001-01 active groups and placebo and the associated pooled SD of 16.893% in hs-CRP at Week 4 from the final analysis of study COR-001-SC1, a sample size of 54 per group yields more than 99% power with 2-sided alpha=0.05. Taking into consideration the dropout rate of 10% by the end of the study, a sample size of 60 per group is planned for this study

Approximately 240 patients (60 per group) will be randomized.

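### For the absolute vital-sign and ECG thresholds, only subjects with a normal baseline can be counted but all assessed subjects form the denominator, so the percentages understate the risk among those who could have the event

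*Protocol*

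**What the plan says.** Protocol section 11.4.5.4 (12-lead ECG) reports how many patients, and what percentage, pass the absolute and relative limits of Table 7. It divides by everyone assessed before and after treatment start: "the denominator will be the number of subjects with a baseline and at least 1 post-baseline assessment within the analysis period". What it counts above the line is narrower, because a baseline condition is added: "the numerator will be the number of subjects with normal baseline with respect to the specific criterion and at least 1 post-baseline outlier value". Section 11.4.5.3 (Vital Signs) applies the same two definitions, in the same words, to Table 6.

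The two tables hold 14 rows of two kinds:

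- **Absolute limits (nine rows):** SBP >160 and <90 mmHg, heart rate >100 and <50, respiration rate >24, PR >200 msec, and QTcF >450, >480 and >500 msec.
- **Change from baseline (five rows):** SBP change of more than 25%, BMI up or down by more than 10%, and QTcF increase of more than 30 and more than 60 msec.

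The rule does not distinguish between the two kinds, and nothing elsewhere in the protocol narrows the denominator.

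**The concern.** A percentage reads as a risk when everyone in the denominator could have been counted in the numerator. In the nine absolute rows that fails. A subject with QTcF above 450 msec at baseline is carried in the denominator of that row but is barred from its numerator.

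Two things follow. Within every arm, the figure is lower than the risk among subjects who started inside the limit, and the shortfall differs from row to row with the share who started outside it. Between arms, a chance difference in that share shifts the contrast even when the risk is the same.

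Section 3.1.2 lists vital signs and ECG by treatment group and dose among the safety assessments, and section 2 says the trial is meant to select a dose for a possible cardiovascular outcome trial. The exclusion criteria set no limit on PR, QTc or heart rate, so baseline values beyond those thresholds are not screened out.

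**Working it through.** **Inputs from the protocol.** The numerator and denominator are those of sections 11.4.5.3 and 11.4.5.4. Arm size is from section 11.1: "Approximately 240 patients (60 per group) will be randomized". It reproduces: 54 / (1 - 0.10) = 60. The protocol states no outlier rate, so there is no figure of its own to reproduce on this point.

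**Assumed inputs.** q, the share abnormal at baseline on a criterion, is taken from 5% to 40%. r, the risk of a new outlier among subjects normal at baseline, is taken as 10% and 20%. The protocol gives neither.

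**Step 1: what each row estimates.** With n assessed subjects, n(1-q) are normal at baseline and n(1-q)r of them are expected to cross the limit.

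- Protocol percentage: n(1-q)r / n = r(1-q)
- Percentage among subjects at risk: n(1-q)r / [n(1-q)] = r
- Relative understatement: 1 - r(1-q)/r = q

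Example with n = 60, r = 20%, q = 20%: 48 subjects are at risk and 9.6 events are expected. The protocol shows 9.6/60 = 16%; the at-risk figure is 9.6/48 = 20%.

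| q | Shown if r = 20% | Shown if r = 10% |
|---|---|---|
| 5% | 19.0% | 9.5% |
| 10% | 18.0% | 9.0% |
| 20% | 16.0% | 8.0% |
| 30% | 14.0% | 7.0% |
| 40% | 12.0% | 6.0% |

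**Step 2: between arms.** With the same r in both arms, the difference shown is r times the difference in q. At r = 20%, a 10-point imbalance gives 0.20 x 10 = 2 points (for example q = 10% against 20% shows 18% against 16%). At r = 10% it gives 1 point. A small real difference can also vanish: r = 20% with q = 30% and r = 17.5% with q = 20% both show 14%.

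**Step 3: how large an imbalance is plausible.** Under randomization the standard deviation of the difference in q between two arms of 60 is sqrt[2q(1-q)/60]: 5.5 points at q = 10%, 7.3 at 20% and 8.4 at 30%. Ten points is thus between 10/8.4 = 1.2 and 10/5.5 = 1.8 standard deviations, which is unremarkable.

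**Step 4: which rows.** On a change-from-baseline criterion nobody can be abnormal at baseline, so q = 0 and nothing is diluted. For SBP >160, exclusion 14 removes patients whose average screening SBP exceeds 160 mmHg. q should be small there, though not necessarily zero, since section 11.3.3 takes the latest pre-dose value as baseline. The other eight absolute rows have no comparable entry limit.

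**The case against.** The best defence is that the protocol's figure is a properly defined quantity: the crude share of all assessed subjects who newly crossed a limit. The rule is explicit and applies alike to every arm. That stands. A reader might infer that the percentage has no defined population, and the text does not support this, because the denominator is stated. The point is narrower: the figure is not the risk among subjects who could have the event, and a reader of a treatment-emergent outlier table is likely to take it as such.

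A reader might also infer that all the outlier percentages are diluted. They are not: the five change rows are sound. Even among the absolute rows the exclusion works row by row. A subject between 450 and 480 msec at baseline can still count under QTcF >480 and >500, and under the increase rows, so worsening does not disappear from view.

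The strongest over-reading is that the rule creates large false differences between arms. Randomization equalises q in expectation, so there is no systematic between-arm bias. An imbalance such as 20% against 40% would be about 20/8.4 = 2.4 standard deviations at 60 per arm. The 2-point shift from a 10-point imbalance is also small beside ordinary sampling error: with 16% shown in each arm, the standard error of the difference is sqrt(2 x 0.16 x 0.84/60) = 6.7 points.

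Finally, these are descriptive tables, counts appear beside the percentages, and ECG intervals and interpretation are also summarised by visit. This limits the consequences but does not remove the mismatch. Nor is it a detail left to the SAP, because the protocol itself fixes the rule.

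**Conclusion.** The point holds for the absolute-threshold rows. For SBP <90, heart rate >100 and <50, respiration rate >24, PR >200, and QTcF >450, >480 and >500, the percentage is r(1-q) and falls short of the at-risk risk by the relative amount q. SBP >160 is affected to a small extent only. The understatement is systematic within each arm and always runs toward a lower figure. The between-arm effect comes only from chance imbalance and is modest.

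The algebra needs no assumption. The sizes do: 18% to 14% in place of 20% rests on assumed values of r = 20% and q = 10% to 30%. A reader might suppose that baseline abnormality is common in stage 3-5 CKD with high cardiovascular risk, but the protocol gives no prevalence, so the true q could be small for several rows. The primary analysis, the sample size and the formal testing are not touched. It is a limited defect in the safety tables, worth correcting because the correction is cheap.

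**What to change.** In sections 11.4.5.3 and 11.4.5.4, split the denominator rule by type of criterion. For absolute thresholds, use subjects with a normal baseline on the specific criterion and at least one post-baseline assessment in the analysis period. For change-from-baseline criteria, keep all subjects with both a baseline and a post-baseline value. Each absolute row then estimates r whatever q is. Print the row-specific denominator, since it will differ between rows.

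The cost is one sentence in each of two sections and a change to the table shells. No new data are needed, and no other analysis changes. How to display subjects who were already abnormal at baseline can be left to the SAP.

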**Table 7 Pre-defined Threshold Value for ECG**

Parameter	Criteria
PR Interval	>200 msec
QTcF	>450 msec
QTcF	>480 msec
QTcF	>500 msec
QTcF	Increase from baseline >30 msec
QTcF	Increase from baseline >60 msec

#### 11.4.5.5 Physical Examination

Physical examination clinically significant new or worsening findings will be reported as adverse events and will therefore be summarized as described for adverse events.

#### 11.4.5.6 Antibodies to Ziltivekimab

The immunogenic potential of Ziltivekimab will be assessed by summarizing the number and percentage of patients who develop detectable anti-drug antibodies (ADA). Anti-drug antibody titers will be summarized descriptively for ADA positive samples and the impact of ADA on PK will be assessed if data allows.

#### 11.4.5.7 Bleeding Events

Bleeding events will be classified using the TIMI Bleeding Classification in [Table 8](#).

**Table 8 TIMI Bleeding Classification**

Parameter	Criteria
Major	Intracranial hemorrhage or a $\geq 5$ g/dl decrease in the hemoglobin concentration or a $\geq 15\%$ absolute decrease in the hematocrit
Minor	Observed blood loss: $\geq 3$ g/dl decrease in the hemoglobin concentration or $\geq 10\%$ decrease in the hematocrit. No observed blood loss: $\geq 4$ g/dl decrease in the hemoglobin concentration or $\geq 12\%$ decrease in the hematocrit
Minimal	Any clinically overt sign of hemorrhage (including imaging) that is associated with a $<3$ g/dl decrease in the hemoglobin concentration or $<9\%$ decrease in the hematocrit
All TIMI definitions take into account blood transfusions, so that hemoglobin and hematocrit values are adjusted by 1 g/dl or 3%, respectively, for each unit of blood transfused. Therefore, the true change in hemoglobin or hematocrit if there has been an intervening transfusion between two blood measurements is calculated as follows: $\Delta$ Hemoglobin = [baseline Hgb – post-transfusion Hgb] + [number of transfused units]; $\Delta$ Hematocrit = [baseline Hct – post-transfusion Hct] + [number of transfused units $\times$ 3].	
TIMI = Thrombolysis In Myocardial Infarction. Source: Rao 2006	

#### 11.4.6 Pharmacokinetic Analysis and Pharmacokinetic/Pharmacodynamic Analysis

##### 11.4.6.1 Pharmacokinetic Data

A listing of PK blood sample collection times as well as derived sampling time deviations will be provided. A patient listing of all serum concentration-time data for each dose group will be presented. Ziltivekimab serum concentrations will be summarized by dose group and

nominal time point, using appropriate descriptive statistics (e.g., n, arithmetic mean, standard deviation (SD), coefficient of variation (CV), minimum, median, maximum, geometric mean, and geometric CV (GCV).

For IL-6, results of PK parameters such as  $C_{max}$ , AUC, and  $T_{1/2}$  will be summarized by dose group.

Individual and mean concentration-time profiles will be presented graphically.

The data from this study may be used in combination with data from other studies to develop a population PK model. If performed, the plan for and results of such analysis will be documented separately.

Pharmacokinetic analysis will be performed separately.

#### **11.4.6.2 Pharmacokinetic/Pharmacodynamic Analysis**

Pharmacokinetic-pharmacodynamic (PK-PD) model parameters will be derived using plasma IL-6 levels to describe target engagement, with clinically meaningful PD variables that may include one or more of the following: C-reactive protein, serum amyloid A, transferrin saturation, hemoglobin, reticulocyte hemoglobin content, or reticulocyte count. The specific model parameters to be estimated will be determined based on review of the observed data. The PD endpoints to be included in the PD analysis will be determined following review of the study data.

A listing of PD blood sample collection times as well as derived sampling time deviations will be provided. A patient listing of all PD results and their corresponding change from baseline value for each dose group will be presented. The observed and change from baseline serum results will be summarized using descriptive statistics by dose group.

Graphical presentations, as appropriate for PD variables, may include: individual observed and percent change from baseline serum concentration-time curves for each patient on linear scale; arithmetic mean serum concentration-time curves by dose group on linear scale.

#### **11.4.7 *Exploratory Analyses of Efficacy and Safety Endpoints Based on Baseline Hemoglobin ( $\geq 11$ or $< 11$ g/dL).***

Exploratory analyses may be performed for the primary and secondary efficacy endpoints with a stratified analysis by baseline hemoglobin ( $\geq 11$  or  $< 11$  g/dL) and CKD stage (3, 4 or 5).

#### **11.5 *Interim Analyses***

Interim analyses will not be conducted.

**12 STUDY COMMITTEES**

**12.1 Clinical Events Committee**

An independent external Clinical Events Committee (CEC) will not be established based on the low current event rates in this ongoing trial.

**12.2 Safety Assessment Committee (SAC)**

A Safety Assessment Committee (SAC) will not be required because the study will be unblinded after 13 weeks for the primary analysis, and all safety data will be reviewed at that time by Sponsor including any potential changes to the ziltivekimab development program if necessary. At the 13-week analysis, only a small internal group of staff at Corvidia and the CRO who are uninvolved with running the study will know the results. The sites, Corvidia and CRO study teams, [REDACTED] study team, CRAs, Investigators and patients will remain blinded to treatment for the duration of the trial.

## **13 INVESTIGATOR AND ADMINISTRATIVE REQUIREMENTS**

### **13.1 Institutional Review Board or Independent Ethics Committee**

The protocol and informed consent for this study must be reviewed and approved by an appropriate IRB or IEC before patients are enrolled in the study. It is the responsibility of the Investigator to assure that the study is conducted in accordance with current country and Local Regulations, International Conference on Harmonisation (ICH), GCP, and the Declaration of Helsinki. A letter, documenting the approval that specifically identifies the protocol by number and title as well as the Investigator, must be received by Corvidia Therapeutics before initiation of the study. Amendments to the protocol will be patient to the same requirements as the original protocol.

After the completion or termination of the study, the Investigator will submit a report to the IRB or IEC.

### **13.2 Informed Consent**

Each potential subject must be provided with oral and written information from the investigator (or other study staff who are conducting the informed consent interview) to allow for an informed decision about participation in the clinical investigation, facilitating the potential subject's comprehension of the information, providing adequate opportunity for the potential subject to ask questions and to consider whether to participate, obtaining the potential subject's voluntary agreement to participate and continuing to provide information as the clinical investigation progresses or as the subject or situations requires. The process must provide sufficient time for subjects to consider the information and providing time and opportunity for the subjects to ask questions and have those questions answered. The investigator (or other study staff who are conducting the informed consent interview) and the subject should exchange information and discuss the contents of the informed consent. This process must occur under circumstances that minimize the possibility of coercion or undue influence. Each patient must be provided with oral and written information describing the nature and duration of the study and must sign a written ICF in a language in which the patient is fluent before study specific procedures are conducted. The signed and dated ICF will be retained with the study records. Each patient will also be given a copy of their signed ICF.

### **13.3 Supplementary Documentation**

Before initiation of the study, the Investigator must provide Corvidia Therapeutics with the following documents (copies of which must be maintained by the Investigator):

1. Curriculum vitae of the Investigator and any sub-Investigators listed on the 1572 form;

2. A signed copy of the IRB or IEC approval notice for protocol and informed consent;
3. A copy of the IRB or IEC approved ICF;
4. Laboratory certification with a list of normal values for laboratory tests that will be conducted at local laboratories;
5. Completed financial disclosure form for the Investigator and any sub Investigators listed on the 1572 form.

#### **13.4 Data Reporting and Case Report Forms**

Data for each patient will be entered into the CRF and verified by the Investigator. It is the Investigator's responsibility to ensure the accuracy, completeness, legibility, and timeliness of the data reported on the patient's CRF. Source documentation supporting the CRF data should indicate the patient's participation in the study and should document the dates and details of study procedures, AEs, and patient's clinical status.

The Investigator or designated representative should complete the CRF as soon as possible after information is collected, preferably on the same day that a study patient is seen for an examination, treatment, or any other study procedure. Any outstanding entries must be completed immediately after the final examination. CRF data will be processed in a US 21 Code of Federal Regulations (CFR) Part 11-compliant system.

#### **13.5 Retention of Data**

U.S. Federal regulations require that a copy of records (e.g., laboratory data slips, source documents, test article disbursement records), which support case records of this study, must be retained in the files of the responsible Investigator for a minimum of 2 years after notification by the Sponsor that the FDA has approved a marketing application for the drug and indication being investigated, or the investigation has been terminated.

#### **13.6 Deviation from the Protocol**

The Investigator will not deviate from the protocol. In medical emergencies, the Investigator will use medical judgment and will remove the patient from immediate hazard, and then notify the Corvidia Therapeutics Medical Monitor and the IRB or IEC immediately regarding the type of emergency and course of action taken. Any action in this regard will be recorded on the appropriate CRF. Any other changes or deviations in the protocol will be made as an amendment to the protocol and must be approved by Corvidia Therapeutics and the IRB or IEC — before the changes or deviations are implemented. Corvidia Therapeutics will not assume any responsibility or liability for any deviation or change.

### **13.7 Study Monitoring**

The Investigator will allow representatives of Corvidia Therapeutics to periodically audit (at mutually convenient times before, during, and after the study has been completed) all CRFs and relevant portions of office, clinical, and laboratory records for each patient. Appropriate source documents such as a record of the patient's medical history and concomitant medications from the patient's physician must be available to confirm eligibility for the study. The monitoring visits provide Corvidia Therapeutics with the opportunity to evaluate the progress of the study; verify the accuracy and completeness of CRFs; assure that all protocol requirements, applicable regulations, and Investigator's obligations are being fulfilled; and resolve any inconsistencies in the study records.

### **13.8 Drug Accountability**

The Investigator must maintain accurate records of the amounts and dates Study Drugs were received from Corvidia Therapeutics and dispensed to the patients, including the remaining volume after dose administration. All drug supplies must be accounted for at the termination of the study and a written explanation provided for any discrepancies. All partially used or unused drug supplies will be destroyed at the site, in accordance with approved written procedures, or returned to Corvidia Therapeutics after written authorization is obtained from Corvidia Therapeutics. The Investigator will maintain a record of the amount and dates when unused supplies were either destroyed or returned. All records will be retained as noted in [Section 13.5](#).

### **13.9 Disclosure of Data**

Individual patient medical information obtained as a result of this study is considered confidential and disclosure to third parties other than those noted below is prohibited. Patient confidentiality will be further assured by utilizing patient identification code numbers to correspond to treatment data in the computer files. The study personnel, employees of the regulatory agencies, including the U.S. FDA and the study sponsor, Corvidia Therapeutics, and its agents will need to review patient medical records in order to accurately record information for this study. If results of this study are reported in medical journals or at meetings, the patient's identity will remain confidential.

